9.6.4 Subgroup Analysis

[The study investigator(s) should describe subgroups motivated by the current understanding of the study outcomes in this section.]

If relevant to specific events, the presence of effect modification by relevant variables (age at vaccination, specific comorbidities, concomitant vaccinations) should be assessed using stratification and statistically by testing for interaction.

9.6.5 Sensitivity Analysis

Sensitivity analysis should focus on the robustness of results to assumptions of the study design and availability of key data elements and should be conducted for the rapid assessment and signal evaluation studies and may include the following:

- If the risk window is not well known, conduct analyses with alternative risk intervals and/or washout periods between the risk and comparison windows
- If exact dates of events are unknown and some are imputed (e.g., if the onset of the event could be prior to date assigned by case validation), conduct analyses lagging the event date.
- If time-varying confounders are not fully available in all data sources, restrict the analysis to sites where data are available on these time-varying confounders and assess at the impact of removing time-varying confounders

9.7 Quality Control

Standard operating procedures or internal process guidance at each research centre should be adhered to for the conduct of the study. These procedures should include internal quality audits, rules for secure and confidential data storage, methods to maintain and archive project documents, quality-control procedures for programming, and standards for writing analysis plans.

This section should describe the study-specific process for programming quality control (e.g., independent programming and/or review of summary output and programming logs by a second programmer), and procedures for data storage, archiving, and backup at each study centre. Also described should be processes for review and quality control of study documentation and reporting of pooled results across research centres.

Note to future investigators: The pandemic has led to changes in healthcare utilization and provision which are likely to extend into the vaccine roll-out period. This may be reflected in observational data as an excess of code counts for a subset of AEsI and/or their proxies in the pandemic period, or as a deficit for others. In order to understand these changes to the data available for analysis, it is recommended that counts and rates of both individual codes utilized in any event case-identification algorithm as well as the set(s) of codes chosen to identify each event be described over time both within and between databases, taking into account the type of database and the type of healthcare encounters typically captured (general practice vs. hospitalization). These counts and rates should be compared graphically in order to aid interpretation of study results.

9.8 Limitations of the Research Methods

The different proposed study designs are subject to limitations due to both the study design and secondary use of health care data.

Data-related limitations include dependency on the accuracy of codes and algorithms to identify outcomes, and the opportunity to confirm events. Misclassification of events (both diagnosis and date of onset) may be minimised by conducting validation and assessing certainty by using BC event definitions. However, the

use of medical records and other secondary data sources for validation purposes may limit the ability to apply Brighton Collaboration criteria and other standardised case definitions to confirm outcomes and to identify true onset of the outcomes.

Exposure ascertainment may be based on pharmacy dispensing records, general practice records, immunization registers, medical records, vaccination cards, or other data sources. The ability to identify specific COVID-19 vaccines and dates of vaccination are currently unknown as it is not clear how the vaccines will be rolled out and what level of detail will be recorded. ACCESS promotes the recording and identification of vaccine brands and batch numbers/ lot numbers. It is likely that subjects vaccinated outside of the healthcare system may not have a record of their vaccination. If brands cannot be distinguished, there may be misclassification of exposure which is of essence due to the differences in platforms and adjuvants. Inability to distinguish lots would misclassify exposure and would be important if any safety signal is related to vaccine production.

Cohort studies are usually less suitable to assess rare events. However, the use of secondary data collection allows for the inclusion of large sample size and increases the statistical power for small risk characterization. A main limitation relates to risk of immortal time bias when inclusion is based on the presence of a certain period of follow-up.

Unvaccinated subjects may become exposed to COVID-19 vaccine at any time over the course of study, censoring in the follow-up time may create an imbalance in the observation periods between vaccinated and unvaccinated groups, which is not random. Another important limitation relates to residual confounding due to unmeasured confounders as it is unlikely that the data sources will comprise information on all potential confounders.

Case -control studies using health care data sources have the advantage of having recorded vaccination prior to case occurrence. Matching and restriction should be applied to deal with confounding. Main sources of bias could be selection bias (e.g. validation cannot be performed for all cases) and is related to exposure, or if validation is conducted in an unblinded manner.

The main strengths of self-controlled designs are the adjustment for time-invariant covariates and their suitability to assess acute events. For less acute events and long latency events, a long washout period will be required and any uncertainty about risk periods will lead to misclassification and attenuation of risk estimates. A major limitation of the CCO is that it should not be used if there are temporal trends in exposure.

9.9 Other Aspects

This section, which is optional, should contain information on any other aspect of the research method not covered by previous sections, such as scientific advisory board or endpoint adjudication committees.

10 Protection of Human Subjects

The proposed studies are non-interventional studies re-using health care data. All data collected in the study will be de-identified with no breach of confidentiality with regard to personal identifiers or health information. Each data access provider should apply for an independent ethics committee review according to local regulations and the local DPIA should be informed. Data protection and privacy regulations (GDPR) should be respected in collecting, forwarding, processing, and storing data from study participants.

11 Management and Reporting of Adverse Events/Adverse Reactions

Aggregate analysis of database studies can identify an unexpected increase in risk associated with a particular exposure. Such studies may be reportable as study reports, but typically do not require reporting of individual cases. Moreover, access to automated databases does not confer a special obligation to assess and/or report any individual events contained in the databases. Formal studies conducted using these databases should adhere to these guidelines.

For non-interventional study designs that are based on secondary use of data, such as studies based on medical chart reviews or electronic health care records, systematic reviews or meta-analyses, reporting of adverse events/adverse drug reactions is not required. Reports of adverse events/adverse drug reactions should only be summarised in the study report, where applicable (EMA, 2017)

According to the EMA Guideline on Good Pharmacovigilance Practices (GVP), Module VI – Management and Reporting of Adverse Reactions to Medicinal Products (EMA, 2017),

“All adverse events/reactions collected as part of [non-interventional post-authorisation studies with a design based on secondary use of data], the submission of suspected adverse reactions in the form of [individual case safety reports] is not required. All adverse events/reactions collected for the study should be recorded and summarised in the interim safety analysis and in the final study report.”

Module VIII – Post-Authorisation Safety Studies, echoes this approach (EMA, 2020). The new legislation further states that for certain study designs such as retrospective cohort studies, particularly those involving electronic health care records, it may not be feasible to make a causality assessment at the individual case level.

12 Plans for Disseminating and Communicating Study Results

In its Guidelines for GPP, ISPE contends that “there is an ethical obligation to disseminate findings of potential scientific or public health importance” (ISPE, 2015); for example, results pertaining to the safety of a marketed medication. “...the marketing authorisation holder should communicate to the Agency and

the competent authorities of the Member States in which the product is authorised the final manuscript of the article within two weeks after first acceptance for publication.”

Protocols should be registered at the EU PAS register and comply with ENCePP or ADVANCE code of conducts. According to both codes of conducts

Study results will be published following guidelines, including those for authorship, established by the International Committee of Medical Journal Editors (ICMJE, 2019). When reporting results of this study, the appropriate Strengthening the Reporting of Observational Studies in Epidemiology (STROBE) checklist will be followed (STROBE, 2015), and recommendations on reproducible reporting of electronic health care data base studies should be followed (Wang, 2017)

Communication via appropriate scientific venues will be considered.

[To be completed or modified by study investigator(s), as needed.]

13 Other Good Research Practice

This study will adhere to the *Guidelines for GPP* and has been designed in line with the European Network of Centres for Pharmacoepidemiology and Pharmacovigilance (ENCEPP) *Guide on Methodological Standards in Pharmacoepidemiology* (ENCEPP, 2018). The *ENCEPP Checklist for Study Protocols* (ENCEPP, 2018) will be completed (see Annex 2).

The study is a post-authorisation study of vaccine safety and will comply with the definition of the non-interventional (observational) study referred to in the International Conference on Harmonisation of Technical Requirements for Registration of Pharmaceuticals for Human Use tripartite guideline *Pharmacovigilance Planning E2E* (ICH, 2019) and provided in the EMA *Guideline on Good Pharmacovigilance Practices (GVP) Module VIII: Post-Authorisation Safety Studies* (EMA, 2020), and with the 2012 European Union pharmacovigilance legislation, adopted June 19, 2012 (European Commission, 2019). The study will comply with the study reporting requirements specified in Module VIII section VIII.B.6.3.1. “Progress reports” and VIII.B.6.3.2. “Final Study Report” of the *Guideline of Good Pharmacovigilance Practices* (EMA, 2020).

The study will be registered in the European Union Post-Authorisation Study Register (ENCEPP, 2019) before the study implementation commences.

The research team and study sponsor should adhere to the general principles of transparency and independence in the ENCePP Code of Conduct (ENCEPP, 2020) or the ADVANCE code of conduct (Kurz, 2017)

[If desired by the study investigators, the following may be included] The research team will apply for the ENCePP Study Seal (ENCEPP, 2018).

[To be completed or modified by the study investigator(s), as needed. Country-specific study registration requirements may be discussed here, where required.]

14 References

1. Austin, Peter C. "An introduction to propensity score methods for reducing the effects of confounding in observational studies." *Multivariate behavioral research* 46.3 (2011): 399-424.
2. DerSimonian, Rebecca, and Nan Laird. "Meta-analysis in clinical trials." *Controlled clinical trials* 7.3 (1986): 177-188.
3. EMA: European Medicines Agency. Guideline on good pharmacovigilance practices (GVP). Module VI – Collection, management and submission of reports of suspected adverse reactions to medicinal products (Rev 2). 22 November 2017. Available at: https://www.ema.europa.eu/en/documents/regulatory-procedural-guideline/guideline-good-pharmacovigilance-practices-gvp-module-vi-collection-management-submission-reports_en.pdf. Accessed 16 June 2020.

Annex 1. List of Stand-Alone Documents

Number	Document reference number	Date	Title
1	Annex 2	<<MM.DD.YYYY>>	ENCePP checklist for protocols

Annex 2. ENCePP Checklist for Study Protocols

The ENCePP Checklist for Study Protocols can be accessed and downloaded using the following link:
[http://www.encepp.eu/standards and guidances/checkListProtocols.shtml](http://www.encepp.eu/standards_and_guidances/checkListProtocols.shtml)

Annex 3. Criteria to determine whether Cohort, Case-Control, Self-Controlled Case Series, Self-Controlled Risk Interval or Case-crossover Can Be Used for Signal Evaluation

Based on the assumptions and requirements of each design, we provide a decision framework for determining when Cohort, Case-Control, Self-Controlled Case Series (SCCS), Self-Controlled Risk Interval (SCRI), and Case-Crossover (CCO) designs can be used for signal evaluation.

The decision framework described below is based on event criteria. However, the identification of a suitable comparator group (active or unvaccinated) and the ability to identify major confounders should also be considered to determine the appropriate study design (see [section 9.1](#)). Cohort and case-control designs are suitable to assess a majority of events. In general, when the data is already available in electronic health care databases, cohort analysis should be conducted since it will provide absolute and relative risk measures. Case control design may be efficient if additional data needs to be collected or exposure patterns are difficult to track over follow-up time, also they allow for matching on calendar time, which is relevant with strong temporal trends. Because cohort and case control designs use other subjects as comparator, residual confounding due to factors that are not easily measurable in EHR data (such as genetics, habits, socio-economic status, ethnicity) can remain. If this is suspected self-controlled designs may be more suitable, but they require accurate estimation of the risk window and onset of the event.

Decision Framework for Determining Suitability of cohort, case-control, SCCS, SCRI, CCO for signal evaluation

Event criteria	Cohort	Case-control	SCCS	SCRI	CCO
Event latency					
Long latency	✓	✓	○ ^a	✗	✗
Short latency	✓	✓	✓	✓	✓
Outcome onset					
Acute onset	✓	✓	✓	✓	✓
Gradual onset	✓	✓	○ ^a	✗	✗
Ability to define risk period for outcome following exposure					
Can be clearly defined	✓	✓	✓	✓	✓
Cannot be clearly defined	✓	✓	○	✗	✗
Effect of event on likelihood of vaccination					
Event does not affect likelihood of vaccination	✓	✓	✓	✓	✓

Event temporarily decreases or increases likelihood of vaccination	✓	✓	✓	✓	✓
Event is a (permanent) contraindication to vaccination	O ^b	O ^b	O ^b	O ^b	✓
Event censors the period of observation for exposure (e.g., death or an outcome that increases the probability of death such as myocardial infarction)	✓	✓	X	X	✓
Event is independently recurrent	✓	✓	✓	✓	✓
Event is non-recurrent but rare	✓	✓	✓	✓	✓
Event is recurrent, and recurrent events are not independent (e.g., stroke)	✓	✓	O ^c	X	O
Temporal trends in vaccination					
Temporal trends in vaccination are not present during the study period	✓	✓	✓	✓	✓
Temporal trends in vaccination are present during the study period	✓	✓	✓	✓	O

Checkmark indicates design is suitable; X indicates not suitable; O indicates that the study design is possible under certain circumstances.

^a Suitable if prodromal symptoms before diagnosis of the outcome do not cause or prevent vaccination, either temporarily or permanently. To address this potential source of bias, every effort should be made to identify the onset of symptoms from the available data such as medical records, rather than relying on the date of diagnosis.

^b Suitable if the vaccine is given in a single dose. If the vaccine is given in multiple doses, the design is not suitable unless special analytic techniques are applied to handle censored, perturbed, or curtailed post-event exposures.

^c Suitable if appropriate adaptations to the self-controlled case series are applied (Farrington, 2010)

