9.1.3.1 Self-controlled Case Series (SCCS)

Retrospective (multi)-database case-only study that includes subjects who were vaccinated with << COVID-19 vaccine>> and experienced << event>>.

The incidence rate ratio between a period of time hypothesized to be at increased risk due to exposure (“risk window”) and control window (All other time within an individual's observation period, that does not fall within the risk period) is calculated (Figure 3).

Figure 3. Self-Controlled Case Series

[figure not shown]

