9.2.2 Study Period, Population and Follow-up Period

The study population will comprise all persons in the source population that are eligible for the study according to specific inclusion and exclusion criteria (such as study period, design requirements and exclusion of prior events, see generic conditions in **Table 3**).

Eligible individuals should be identified in each of the database using a pre-specified selection process and/or by applying pre-specified algorithms. Attrition diagrams should be made. Follow-up time should start at the moment that the latest of the inclusion criteria is met, follow-up ends at the earliest of the occurrence of censoring conditions or the last data draw down/data availability.

Study period, study population and follow-up period for signal evaluation study designs are summarized in **Table 3**.

Note to future investigators: this section provides general information and should be adapted according to the type of safety study conducted.

Table 3. Study period, study population, and follow-up period by study design

Study design/Analysis Method	Study period	Study population [§]	Follow-up period
Cohort	Index cohort: from <<COVID-19 vaccine>> introduction until last data collected Comparison cohort: from <<COVID-19 vaccine>> introduction until last data collected	Index: all subjects who received at least 1-dose of COVID-19 vaccine Comparison: all subjects matched for covariates such as age, sex, comorbidities, identified from same data source(s) who did not receive COVID-19 vaccine or alternative vaccine.	Start: latest of fulfillment of inclusion criteria or start of study period End: earliest of end of study period or censoring conditions
Case-control	From <<COVID-19 vaccine>> introduction until date protocol is implemented or data is available	Cases: Subjects with a diagnosis of << event>> in the study period. Controls: Subjects matched on age, sex, database and/or region without << event>> diagnosis at the time of index	From start of follow-up until index date The length of risk period ('look back period') should be defined according to the event under evaluation

		date. Index date = index date of the corresponding cases	
SCCS	From <<COVID-19 vaccine>> introduction until latest data available	Subject who received at least 1-dose of COVID-19 vaccine and who experienced <<event>>	Start: latest of fulfillment of inclusion criteria or start of study period End: earliest of end of study period or censoring conditions

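### Annex 3 marks SCCS as unconditionally suitable when the event temporarily changes the chance of vaccination; with SCCS as defined here, the estimate is biased if data are cut during roll-out

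*Protocol*

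**What the plan says.** Annex 3 rates each design against criteria of the event. Its legend reads: "Checkmark indicates design is suitable; X indicates not suitable; O indicates that the study design is possible under certain circumstances".

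- **Row at issue.** "Event temporarily decreases or increases likelihood of vaccination" carries a tick for all five designs, with no O and no footnote. The marks are the same as in the row where the event has no effect on vaccination.
- **Adjacent row** (event is a permanent contraindication). SCCS is O with footnote b. For a multi-dose vaccine the footnote says "the design is not suitable unless special analytic techniques are applied to handle censored, perturbed, or curtailed post-event exposures".
- **Footnote a**, attached to SCCS in the long-latency and gradual-onset rows: "Suitable if prodromal symptoms before diagnosis of the outcome do not cause or prevent vaccination, either temporarily or permanently".

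The SCCS itself is defined elsewhere:

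- Population (Table 3, Section 9.2.2): "Subject who received at least 1-dose of COVID-19 vaccine and who experienced <<event>>".
- Study period (Table 3): "From <<COVID-19 vaccine>> introduction until latest data available".
- Control window (Section 9.1.3.1): "All other time within an individual's observation period, that does not fall within the risk period".

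The SCRI (Section 9.1.3.2) instead takes its control window after the risk window.

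**The concern.** SCCS compares event rates within vaccinated cases and needs the event not to influence whether, or when, the person enters the vaccinated set. This row describes an event that does exactly that.

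Pre-vaccination time is control time, and a case counts only if vaccinated by the data cut. An event that defers vaccination therefore pushes some pre-vaccination cases beyond the cut. They drop out, control events become too few, and the IRR is too high. An event that prompts vaccination pulls in pre-vaccination cases who would otherwise still be unvaccinated at the cut. Control events become too many and the IRR is too low, which can mask a real risk.

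The annex recognises related problems in footnotes a and b but attaches no condition here. The template is meant to be copied into many studies, and Section 7 refers users to Annex 3 for the choice of design, so a wrong mark is repeated.

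**Working it through.** The plan states no IRR, event count or power for this design, so there is no figure to reproduce. The check is the large-sample SCCS estimate when the true IRR is 1.

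**Inputs from the protocol.** Vaccinated cases only; observation from vaccine introduction (day 0) to the cut T; all non-risk time is control. The risk window is 42 days, as in the Guillain-Barré example (Section 9.1.1) and the note to Figure 4.

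**Assumptions not in the documents.** Single dose; event times uniform on (0, T); planned vaccination day V uniform over 180 days; T of 120, 180 or 365; a share p of persons whose event E precedes V change their date, by one of three rules with d = 30, 60 or 90 days:

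1. End of deferral: if V < E + d, vaccination moves to E + d.
2. Whole plan shifted: V becomes V + d.
3. Brought forward: V becomes the earlier of V and a uniform day in (E, E + d).

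**Estimator.** Person i, vaccinated on day v_i < T, has risk time r_i = min(42, T − v_i) and control time c_i = T − r_i. With x_i = 1 if the event falls in the risk window, the IRR θ solves Σ[x_i − θr_i/(θr_i + c_i)] = 0.

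**Direction by hand (T = 120, rule 2, p = 1).** As a share of all simulated cases:

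- Retained, event before vaccination: (120 − d)²/(2·120·180). For d = 0 this is 14,400/43,200 = 0.333; for d = 60 it is 3,600/43,200 = 0.083.
- Retained, event after vaccination: 120²/43,200 = 0.333, whatever d is.
- Of these, in the risk window: (42·78 + 42²/2)/(120·180) = 4,158/21,600 = 0.193.

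Control events fall from 0.333 + 0.333 − 0.193 = 0.474 to 0.083 + 0.333 − 0.193 = 0.224, while risk-window events are unchanged. The IRR must rise. Under rule 3 with d = 30, the retained pre-vaccination share rises instead, from 0.333 to 0.624 in simulation, so the IRR must fall.

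**Null IRR, 1,000,000 simulated cases per scenario (d = 30 / 60 / 90):**

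| Cut | Share affected | Rule 1 | Rule 2 | Rule 3 |
|---|---|---|---|---|
| 120 | all | 1.06 / 1.28 / 1.93 | 1.47 / 2.08 / 2.62 | 0.54 / 0.59 / 0.66 |
| 120 | half | 1.03 / 1.13 / 1.32 | 1.19 / 1.35 / 1.44 | 0.70 / 0.75 / 0.79 |
| 120 | quarter | 1.02 / 1.06 / 1.14 | 1.08 / 1.15 / 1.18 | 0.82 / 0.85 / 0.88 |
| 180 | all | 1.02 / 1.08 / 1.23 | 1.23 / 1.54 / 1.85 | 0.88 / 0.89 / 0.91 |
| 180 | half | 1.01 / 1.05 / 1.10 | 1.11 / 1.21 / 1.30 | 0.94 / 0.95 / 0.95 |
| 365 | any | 0.99–1.01 | 0.99–1.01 | 0.99–1.01 |

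With p = 0 the result is 1.00 to within 0.01. Separate runs agree to 0.01 or 0.02, so the ranges quoted elsewhere are rounded.

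**Different roll-out shape.** With a constant vaccination hazard, 60% coverage and a day-180 cut, no vaccination for 14/30/60/90 days after the event gives 1.07/1.16/1.36/1.59. A hazard raised 3- or 5-fold for 30 days gives 0.82 or 0.72. Shorter risk windows reduce the bias: at the same cut and coverage, 60 days' deferral gives 1.35 with a 42-day window and 1.24 with a 2-day window.

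**Candidate remedies.** With control time after vaccination only, the null IRR is 0.99 to 1.02 in every scenario. Deleting a pre-vaccination window of length d reduces the bias in most scenarios cut during roll-out but leaves 0.79 to 1.35 under the constant-hazard model. It can also overshoot: with roll-out ending at day 180, data to day 365 and a 5-fold hazard for 30 days, the IRR goes from 0.93 to 1.11.

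**The case against.** **No contradiction with footnote a.** A reader might infer that the tick contradicts footnote a. It does not. That footnote concerns prodromal symptoms before diagnosis, sits on the latency and onset rows, and is answered by dating onset better. A correctly dated event that alters later vaccination is a different problem, so the inconsistency is one of principle. Footnote b, on the adjacent row, is the closer comparison.

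**Footnote b clears a single dose.** True, and by analogy a single-dose tick here might seem fair. But the footnote does not say that control time must follow vaccination, and the single-dose result is unbiased only under that restriction.

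**Control time is not settled.** Figure 3 is not available, and follow-up starts when the last inclusion criterion is met, which could be read as the day of the first dose. Against that, Section 9.1.3.1 assigns all non-risk observation time to control, and Table 3 starts follow-up on the day of vaccination for SCRI but not for SCCS. The natural reading includes pre-vaccination time.

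**Other safeguards exist.** All five designs are ticked, Annex 3 generally favours a cohort analysis when data are already available, Section 9.2.3.3 asks for windows by event and design, and Section 9.6.5 suggests washout periods. So the row permits SCCS; it does not steer users to SCCS over the alternatives. None of these provisions addresses event-dependent vaccination.

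**The size is assumed.** This stands. The extremes need an early cut and every pre-vaccination case changing date, whereas the row speaks only of likelihood.

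**Conclusion.** The point holds: the SCCS mark should be conditional. For SCCS as defined in Sections 9.1.3.1 and 9.2.2, a temporary effect of the event on vaccination biases the null IRR when data are cut during roll-out, upward for deferral and downward for prompted vaccination.

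The size is an illustration. Under uniform roll-out over 180 days, a 42-day window and effects of 30 to 90 days, it is about 0.54 to 2.6 at day 120 if all pre-vaccination cases are affected, 0.70 to 1.45 if half are, and 0.94 to 1.31 at day 180 if half are. There is no bias when everyone is vaccinated well before the cut.

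Two stronger readings are not supported. The widest range is not a property of the plan, because the documents fix neither cut, coverage nor strength of effect. Nor does the point extend to every self-controlled design: the SCRI tick is unaffected for a single dose, because its control window follows the risk window. Multi-dose schedules were not computed.

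**What to change.** In the Annex 3 row on temporary effects, change the SCCS mark from a tick to O and add a footnote to this effect: suitable for a single-dose vaccine if control time is taken only after vaccination; otherwise suitable only with a method for event-dependent exposure, as footnote b already requires for multiple doses.

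The footnote should not offer removal of a fixed pre-vaccination window as sufficient, since this reduces the bias in some scenarios but does not reliably remove it.

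The edit is one cell and one footnote. The analytic cost is less control time and therefore wider intervals. For a single dose the restricted SCCS comes close to the SCRI, which is already ticked in this row.

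### Annex 3 footnote b accepts the SCCS for a vaccination-contraindicating event on the strength of a single dose; that holds for the SCRI but not for the SCCS as sections 9.1.3.1 and 9.2.2 most naturally define it

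*Protocol*

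**What the plan says.** The decision framework in Annex 3 has a row headed "Event is a (permanent) contraindication to vaccination". Cohort, case-control, SCCS and SCRI are all rated as possible under certain circumstances, with footnote b. The footnote reads "Suitable if the vaccine is given in a single dose" and continues "If the vaccine is given in multiple doses, the design is not suitable unless special analytic techniques are applied". It sets no condition on where control time lies.

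The SCCS is defined elsewhere:

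- Section 9.1.3.1: control time is "All other time within an individual's observation period, that does not fall within the risk period".
- Section 9.2.2, Table 3, study population: "Subject who received at least 1-dose of COVID-19 vaccine and who experienced <<event>>".
- Table 3, study period: "From <<COVID-19 vaccine>> introduction until latest data available".
- Table 3, follow-up: "Start: latest of fulfillment of inclusion criteria or start of study period".

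The SCRI differs on the feature that matters. Section 9.1.3.2 puts its control window after the risk window, and Table 3 starts its follow-up on the day of vaccination. Table 4 assigns conditional Poisson regression to both designs.

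**The concern.** Footnote b deals with one consequence of a contraindicating event: doses due after the event are not given. With a single dose and observation from vaccination, no later dose is left to lose, so the rule is sound. An SCCS that also counts time before vaccination has a second problem, which does not depend on the number of doses. Someone whose event falls before the planned dose is not vaccinated, so is not a vaccinated case and drops out of the analysis. Those who remain contribute pre-vaccination control time in which an event could not have been retained. The baseline rate is too low and the IRR too high.

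Annex 3 recognises this mechanism elsewhere. Footnote a makes the SCCS depend on prodromal symptoms neither causing nor preventing vaccination, whether for a time or for good. Footnote b then accepts the stronger case, where the event itself prevents vaccination, if there is only one dose.

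The primary objective in section 8 is to determine whether risk is increased after vaccination. A study that chooses its design from Annex 3 could report a raised IRR for a vaccine with no effect on the event. The sensitivity analyses suggested in section 9.6.5 do not include removing pre-vaccination control time, and section 9.8 does not mention event-dependent vaccination.

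**Working it through.** The protocol gives no bias, power or sample-size figure on this point, so there is none to reproduce. The check takes the SCCS as defined and asks what it estimates for a single dose.

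**Inputs from the protocol.** Vaccinated cases only (Table 3); all non-risk observation time as control (9.1.3.1); study period from vaccine introduction (Table 3); conditional Poisson regression (Table 4); a 42-day risk window, used as an illustration in the note to Figure 4.

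**Assumed inputs.** Observation length T (180 or 365 days from introduction); planned vaccination day v; share c of people with a pre-vaccination event who are then never vaccinated (c = 1 is full contraindication); a rare event with constant background rate λ.

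**Closed form, true IRR = 1.** Expected events per person among retained cases:

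- risk window: 42λ
- before vaccination: (1 − c)vλ
- after the risk window: (T − v − 42)λ

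Each retained case contributes 42 days of risk time and T − 42 days of control time. So

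IRR = [42λ / 42] ÷ [λ((1 − c)v + T − v − 42) / (T − 42)] = (T − 42) / (T − 42 − cv).

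| T | v | c = 1 | c = 0.5 |
|---|---|---|---|
| 365 | 30 | 323/293 = 1.10 | 323/308 = 1.05 |
| 365 | 90 | 323/233 = 1.39 | 323/278 = 1.16 |
| 365 | 180 | 323/143 = 2.26 | 323/233 = 1.39 |
| 180 | 30 | 138/108 = 1.28 | 138/123 = 1.12 |
| 180 | 60 | 138/78 = 1.77 | 138/108 = 1.28 |
| 180 | 90 | 138/48 = 2.88 | 138/93 = 1.48 |

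With v = 0 or c = 0 the ratio is exactly 1. It keeps rising as vaccination moves towards the end of observation: T = 180, v = 120, c = 1 gives 138/18 = 7.67. Only 18 days of control time then follow the risk window, so the conclusion does not rest on that extreme.

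**Simulation.** Six million persons per scenario, single dose, vaccination day uniform from 0 to a maximum, conditional Poisson fit. With a uniform roll-out, v in the formula becomes half the maximum.

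| T | roll-out (days) | formula, c = 1 | simulated, true IRR 1, c = 1 | simulated, true IRR 2, c = 1 |
|---|---|---|---|---|
| 180 | 0–130 | 138/(138 − 65) = 1.89 | 1.87 | 3.80 |
| 365 | 0–180 | 323/(323 − 90) = 1.39 | 1.40 | 2.76 |
| 365 | 0–320 | 323/(323 − 160) = 1.98 | 1.97 | 3.98 |

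At c = 0 the fit returned 0.99 to 1.02 when the truth was 1 and 1.99 to 2.03 when it was 2. The method is therefore sound when the event does not affect vaccination.

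**Post-vaccination control time only.** A case vaccinated on day v now contributes 42 risk days and T − v − 42 control days. At true IRR = 1 the expected events are 42λ and (T − v − 42)λ, so the ratio is exactly 1 whatever c is. The simulation gave 0.95 to 1.01 for a true IRR of 1 and 1.93 to 2.05 for a true IRR of 2; the scatter is simulation noise.

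**The case against.** The strongest objection is that the protocol does not fix when SCCS observation starts. Section 9.1.3.1 refers to an observation period without giving its first day, and Table 3 starts follow-up at the later of meeting the inclusion criteria or study start. The cohort row uses the same start wording, and for its index cohort, also defined by at least one dose, that most naturally means the day of vaccination. Read the same way, the SCCS would start at vaccination and the bias would vanish. Figure 3 is not available to settle it.

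Part of this stands: the start is loosely worded. A reader might infer that the protocol expressly prescribes pre-vaccination control time, and it does not. But the vaccination-start reading is the weaker one. The same SCCS cell also requires the event, so by that logic follow-up would start at the event. Table 3 states a vaccination-day start only for the SCRI.

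It can also be said that this is a template to be adapted, that the cell is graded as conditional, and that few studies combine a contraindicating event, a single-dose vaccine and an SCCS. The narrow reach is conceded. The rest does not rescue the footnote: it states the condition under which the design is suitable, and for the SCCS that condition is insufficient. An affirmative design-selection rule is not a detail left for later.

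**Conclusion.** Footnote b is wrong as written for the SCCS and right for the SCRI. Under the most natural reading of section 9.1.3.1 and Table 3, a single dose does not protect the SCCS when the event prevents vaccination. The bias is upward whenever there is pre-vaccination control time and the event stops some people from being vaccinated.

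The direction follows from the definitions; the size does not. Only the 42-day window comes from the protocol. Under the assumed periods, with vaccination on day 30 to 90 of 180 or day 30 to 180 of 365, the null IRR under full contraindication is about 1.1 to 2.9. It is 1 if everyone is vaccinated at introduction or control time is post-vaccination only. The c = 0.5 results describe partial deterrence, which goes beyond the row that footnote b qualifies.

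Two wider conclusions might be drawn, and the documents support neither. One is that every SCCS under this template is biased: with no effect of the event on vaccination the IRR is unbiased, and a purely temporary delay with full catch-up gave 1.00 to 1.02 in simulation, so the Annex 3 row for temporary effects need not change. The other is that every SCCS event needs a second, post-vaccination-only IRR: the error concerns contraindicating events alone.

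**What to change.** 1. In Annex 3, footnote b, separate the SCCS from the other designs. For the SCCS, make single-dose suitability conditional either on observation starting on the day of vaccination, so that control time is post-vaccination only, or on an SCCS extension for event-dependent exposure.
2. Leave the single-dose rule unchanged for the SCRI.
3. In section 9.1.3.1 and the SCCS row of Table 3, state when SCCS observation starts for events that contraindicate vaccination, and that pre-vaccination time is not control time for them unless the extension is used.
4. Optionally, list a post-vaccination-only IRR in section 9.6.5 as a sensitivity analysis where the event may deter vaccination.

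The edits are one footnote and a sentence in each of two places. The statistical cost is less control time, hence wider intervals, for the affected events.
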